1. Protocol Title

A comparison of analgesic efficacy of ultrasound-guided genicular nerve block versus saline injection for total knee replacement: a prospective, randomized controlled trial.

[name], [name]

2. Purpose of the study

To determine if ultrasound-guided genicular nerve blocks with 0.25% bupivacaine and dexamethasone provide improved knee analgesia for patients recovering from primary total knee replacement surgery compared to saline injection.

3. Background and Significance

Total knee arthroplasty is associated with intense early postoperative pain. A sizeable proportion (25–40%) of patients experience severe pain postoperatively despite a comprehensive multimodal analgesic regimen.(1) Enhanced recovery protocols that emphasize early mobilization and hospital discharge remain varied among hospitals. Regional anesthetic techniques have evolved to preserve motor function in an effort to promote early ambulation and hospital discharge, while optimizing sensory blockade for adequate analgesia. The adductor canal blockade (ACB) of the saphenous nerve has demonstrated reduced opioid consumption and preservation of quadriceps muscle strength when compared to placebo and to femoral nerve blockade.(2) However, several studies have shown that despite ACB, many patients may still have at least moderate, movement-related pain. This may be partly because the ACB does not provide analgesia to the posterior aspect of the knee, in which pain is commonly moderate to severe after surgery.

It has been proposed in the literature that complete blockade of the knee joint for adequate analgesia requires blockade of the genicular nerves.(3) The genicular nerves provide sensory innervation to the joint capsule and internal and external ligaments of the knee joint. The superior and inferior medial genicular nerves arise in the posterior popliteal fossa and are sensory branches of the tibial nerve. The superior and inferior lateral genicular nerves are sensory branches of the common peroneal nerve and course anteriorly to the lateral knee. The identification of the genicular nerves using ultrasound has been described in the literature.(4)

At our institution, all patients scheduled to undergo total knee replacement spinal anesthesia as well as infiltration of local anesthetic into the Interspace between the Popliteal Artery and posterior Capsule of the Knee (IPACK) injections as part of their pain management, as this practice provides analgesia while preserving motor function.(5)¹ Postoperatively, all patients receive adductor canal peripheral nerve catheters.

We hypothesize that the combination of ultrasound-guided adductor canal nerve catheter, IPACK block, and single injection genicular nerve blockade will further decrease opioid consumption and pain scores, therefore leading to decreased systemic side effects and improved overall satisfaction compared to ultrasound-guided adductor canal catheter and IPACK block alone in patients undergoing elective minimally invasive TKA surgery.

4. Design and Procedures

This is a single center, prospective, randomized, controlled, single-blinded study. 40 subjects will be recruited (see #6 Recruitment and Compensation below), 20 in each group.

Primary Outcome:

Cumulative opioid consumption at 24 hours.

Secondary Outcomes:

- Quality of analgesia at rest and with movement, as measured by numerical pain rating scores (NRS-11) up to 48 hours (0h, 6h, 24h, 36h, 48h)
- Cumulative opioid consumption at 48 hours
- Opioid consumption and quality of analgesia based on patient diary after discharge on postoperative day 7 (worst pain score)
- Sleep quality based on number of times awakened on the evening of POD#0
- Subject satisfaction with the block technique at 24h and POD#7
- 20 meter walk test time on POD#1. This will be conducted on 6100, the orthopedic floor. Research staff will conduct the test, which will involve the patient walking at his/her fastest pace to a mark on the floor 10m away, then turning around and returning to the start line.

Preoperative Management

Subjects will be randomized on the morning of surgery to receive either genicular nerve blocks using 15mL 0.25% bupivacaine with 2mg dexamethasone or the same blocks with 15 ml of saline.

Prior to the block in the preoperative holding area, all subjects will receive the standard oral multimodal analgesic regimen, a spinal anesthetic with 12.5 mg of bupivacaine, and posterior capsule infiltration with 20 ml of 0.2% ropivacaine. Subjects will then receive the study intervention.

Single injection genicular nerve block technique

The ultrasound-guided genicular nerve block will be performed at the site of the superior lateral, the superior medial, and the inferior medial genicular nerves. The superior lateral genicular nerve is located at the confluence of the lateral femoral shaft and the lateral femoral condyle (in the anteroposterior plane) and at the midpoint of the femur (in the

lateral plane). The superior medial genicular nerve site is located at the confluence of the medial femoral shaft and the medial femoral condyle (in the anteroposterior plane) and at the midpoint of the femur (in the lateral plane). The inferior medial genicular nerve site was located at the confluence of the medial tibial shaft and the tibial flare (in the anteroposterior plane) and the midpoint of the tibia (in the lateral plane). Color Doppler will be used to identify the arterial structures which serve as landmarks for the corresponding nerves. All nerve blocks will be performed by a trainee supervised by an anesthesiologist experienced in regional anesthesia.

After skin local anesthetic infiltration, a 10 cm 21G insulated block needle (Sonoplex, Pajunk Medical Systems, Norcross, GA) will be inserted from the lateral aspect of the ultrasound probe and aligned with the ultrasound scanning plane (in-plane approach). In this way, both the needle shaft and tip can be visualized as the needle approaches the genicular nerve. The needle will be redirected as needed. Once satisfactory position of the needle tip is confirmed and after frequent negative aspiration, 5mL of a solution containing 15 ml of 0.25% bupivacaine with 2mg dexamethasone, or 5mL saline, will be slowly injected. Spread of local anesthetic will be documented adjacent to the target nerve in real time. This procedure will be performed at the site of the three genicular nerves described above.

Subjects will then undergo the surgical procedure. In the post-anesthesia care unit (PACU), all subjects will receive the standard adductor canal continuous catheter that will be connected to a pump containing 0.2% ropivacaine with infusion rate of 8mL/hr.

Intraoperative Management

Subjects will receive a spinal anesthetic using intravenous propofol infusion for sedation. No muscle relaxation will be permitted. In addition, no long-acting opioids will be administered for analgesia; instead, boluses of fentanyl 25 to 50 mcg will be administered as guided by respiratory parameters and/or hemodynamics. Subjects will maintain spontaneous ventilation throughout surgery. Respiratory rate greater than 18 per minute will be treated by administration of 25 to 50 mcg of fentanyl. At the conclusion of the case, the propofol will be discontinued and the subject awakened. Subjects will be transported to PACU. All subjects will receive intravenous fentanyl and/or oral oxycodone as needed for pain management.

Postoperative Evaluation

Evaluation of both pain intensity (NRS-11 pain scale) and interval opioid consumption will be undertaken at the following time points in a blinded fashion by a member of the research team:

- PACU (30-60 minutes after arrival to PACU)
- 6 hours postoperatively
- 24 hours postoperatively

- 36 hours postoperatively
- 48 hours postoperatively
- POD 7 (morning of POD#7)

All data will be recorded in a REDCap database. Subjects will be provided with a diary to record the relevant data elements. Calls will be made on POD 7 to record the data in the research record by a member of the research team.

Sleep quality will also be assessed by a member of the research team on POD#1 as a function of the number of times the patient was awoken by pain.

Occurrences of adverse events reported by subjects will also be collected during the phone interview on POD#7. Subjects will be queried as to any block related complications (e.g., prolonged motor blockade or numbness) and opioid-related adverse events. Satisfaction with the postoperative pain management experience will also be graded on a 0-10 point scale on POD#7.

5. Selection of subjects

Criteria for inclusion:

- Subjects scheduled for primary elective total knee arthroplasty
- Age 56-85 years of age
- American Society of Anesthesiologists Physical Status I-III
- BMI 18-40 kg/m²

Criteria for exclusion:

- Inability to cooperate with protocol
- Inability to understand or speak English
- Allergy to ropivacaine, bupivacaine or other local anesthetic
- Contraindication to peripheral nerve block (e.g. local infection, neurologic deficit or disorder, previous trauma or surgery to ipsilateral knee, etc.)
- Revision knee surgery
- Chronic opioid consumption (daily morphine equivalent of >30 mg for at least four weeks prior to surgery)
- History of chronic pain
- History of psychiatric disorder
- History of diabetes mellitus with documented or symptomatic peripheral neuropathy

6. Subject recruitment and compensation

Potential subjects (see inclusion criteria above) will be identified on the surgical schedule several days in advance of the surgical procedure. These individuals will be contacted by telephone and asked for permission to discuss the study. The purpose of the study will be explained, the consent form read out loud, and any questions answered. Potential subjects will be encouraged to take time to discuss the study with family, and will be told

that there will be additional time to answer any questions on the day of surgery. Potential subjects will be told that there is no obligation to take part in the study and their decision will not affect the quality of their care.

On the day of surgery, one of the investigators will approach the potential subject in the preoperative area and answer any remaining questions. Subjects that indicate their interest in participating will then sign an informed consent and complete a HIPAA authorization form. There will be no compensation for subjects for their participation.

7. Consent process

The consent process will be conducted by one of the physician investigators involved in the study. The consent process will take place in the pre-operative area. Throughout the consent process, measures will be taken to maintain privacy, such as conducting face-to-face conversations in private rooms. As much time as necessary will be spent with each potential subject to sufficiently explain and answer all questions, and address all concerns they may have in regard to the study and/or consent process.

8. Subject's Capacity to Give Legally Effective Consent

Subjects who do not have the capacity to give legal consent will not be approached for participation in this study.

9. Study interventions

See #4.

10. Risk/benefit assessment

Risk to the subject

This study involves a single injection genicular nerve block, either with a local anesthetic solution or saline. Risks associated with the nerve block include bleeding, infection, and nerve damage.

Benefits to the subject

There are no direct benefits to the subject. There is potential for improved pain control if the subject is randomized to the treatment arm.

11. Costs

There will be no costs to the subject for participation in the study. Subjects will not be compensated for their participation.

12. Data analysis and statistical considerations

Based on our institutional experience with primary total knee arthroplasty and postoperative opioid consumption, we calculate that 20 patients per group (total of 40) will be required to detect a 30% difference in our primary outcome measure.

Baseline patient demographic and clinical characteristics as well as surgical factors will be compared between treatment groups. The difference in the primary outcome, 24h

opioid consumption, will be assessed via two-sided two-sample t-test. Outcome data distribution will be assessed for normality and log-transformed if necessary. If differences in key patient factors are identified between groups we will pursue a multivariable linear model in order to control for potential confounding of treatment effect estimates. Secondary numeric outcomes of pain score and opioid consumption at 48 hours and post-op day 7 will be compared via t-tests or Mann-Whitney tests as appropriate. Sleep quality during the night of surgery will be assessed via poisson regression of the count of times awakened from sleep. Subject satisfaction with the block technique will be compared using a t-test or Mann-Whitney test as appropriate.

13. Data & Safety Monitoring

In accordance with federal regulations the PI will monitor for, review, and promptly report to the IRB, appropriate institutional officials, sponsor, coordinating center and the appropriate regulatory agency head all unanticipated problems involving risks to subjects or others that occur in the course of a subject's participation in a research study (45 CFR 46.103(b)(5)(i) and 21 CFR 56.108(b)(1)), all AE reports will be reported per the DUHS IRB policies. PI will be monitoring all AEs and submitting reports to the IRB per DUHS IRB policy.

14. Privacy, Data Storage and Confidentiality

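### Fewer systemic side effects are part of the hypothesis, but they are not a listed outcome, have no planned comparison, and are asked about on schedule only by telephone on POD#7

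*Combined protocol and SAP*

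**What the plan says.** The hypothesis at the end of Section 3 of the combined protocol and SAP says that adding the genicular block will lower opioid consumption and pain scores, "therefore leading to decreased systemic side effects and improved overall satisfaction".

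Section 4 names the primary outcome as "Cumulative opioid consumption at 24 hours". It lists six secondary items: pain scores to 48 h, 48 h opioid consumption, diary-based opioid use and worst pain at day 7, sleep, satisfaction ("Subject satisfaction with the block technique at 24h and POD#7") and a POD#1 walk test. None is a side-effect or adverse-event outcome.

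Under Postoperative Evaluation in Section 4, the timed assessments are described as follows: "Evaluation of both pain intensity (NRS-11 pain scale) and interval opioid consumption will be undertaken at the following time points". The times are PACU, 6, 24, 36 and 48 h, and POD 7. Adverse events come in separately: "Occurrences of adverse events reported by subjects will also be collected during the phone interview on POD#7". The content of that call is: "Subjects will be queried as to any block related complications (e.g., prolonged motor blockade or numbness) and opioid-related adverse events". The diary is described only in general terms: "Subjects will be provided with a diary to record the relevant data elements".

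Section 12 gives analyses for opioid use, pain, sleep and satisfaction, and none for side effects or adverse events. Section 13 covers safety oversight: "PI will be monitoring all AEs and submitting reports to the IRB per DUHS IRB policy".

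**The concern.** The hypothesis names four benefits: less opioid, less pain, fewer side effects and better satisfaction. Three of them have a listed outcome and a planned analysis. Side effects have neither.

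The timing of collection adds to the problem. The expected mechanism is that less opioid leads to fewer opioid effects, and the main opioid outcomes are measured at 24 and 48 h. The side-effect question comes once, on day 7. It names no opioid-related events and sets no grading and no time window. A patient who reports nausea in that call may mean the first evening or the day before the call. A patient who is not reached gives no scheduled side-effect data at all.

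At stake is one explicit clause of the hypothesis. A statement in the trial report about side effects would rest on a comparison that was not prespecified, using events that cannot be placed in time.

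**Working it through.** **The plan's own figure.** Section 12 gives 20 per group to detect a 30% difference in the primary outcome. Alpha, power, mean and SD are not stated, so the figure cannot be reproduced. Inverting the two-means formula with two-sided alpha 0.05 and 80% power (both assumed) gives SD/mean = 0.30 / [(1.960 + 0.842) × √(2/20)] = 0.30 / 0.886 = 0.34. The present point does not depend on this. Only the 20 per arm is carried forward.

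**Hypothesis against outcomes and analysis.**

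| Benefit in the hypothesis (Section 3) | Listed outcome (Section 4) | Planned analysis (Section 12) |
|---|---|---|
| Less opioid | Yes: 24 h, 48 h, day 7 | Yes |
| Less pain | Yes: five times to 48 h, and day 7 | Yes |
| Better satisfaction | Yes: 24 h and POD#7 | Yes |
| Fewer systemic side effects | No | No |

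**Timing.** Counting surgery as day 0, the 24 h assessment falls on day 1 and the 48 h assessment on day 2. The call is on day 7. The gap is 7 − 1 = 6 days from the primary endpoint and 7 − 2 = 5 days from the 48 h outcome. Section 4 has post-discharge opioid use recorded in a diary, so the protocol itself expects further opioid exposure before the call. Sleep is handled differently: awakenings on the night of surgery are asked about on POD#1.

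**What a side-effect outcome could show with 20 per arm.** The documents give no event rates, so those below are assumptions. Each patient counts once (any event to 48 h, yes or no), however many times the checklist is completed.

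The 95% CI half-width for a difference in proportions is 1.96 × √[p₁(1 − p₁)/20 + p₂(1 − p₂)/20].

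- 50% v 30%: 1.96 × √(0.25/20 + 0.21/20) = 1.96 × √0.0230 = 0.297, or about ±30 percentage points.
- 40% v 28%: 1.96 × √(0.24/20 + 0.2016/20) = 1.96 × √0.02208 = 0.291, or about ±29 points.

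Exact Fisher power is the sum of the binomial probabilities of all pairs of counts with a two-sided Fisher p-value of at most 0.05:

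- 50% v 30% (a 40% relative reduction): 0.163.
- 40% v 28% (a 30% relative reduction, the same relative size as the planned opioid difference): 0.075.
- Over assumed control rates of 20% to 60% with a 30% relative reduction: 0.038 to 0.117.

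A significance test would be uninformative in this range. An estimate with its interval is what the design can support.

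**The case against.** The strongest reply is that side effects are a downstream expectation and not the research question. Section 2 asks only whether the block improves knee analgesia. Opioid-related events are asked about in every subject on POD#7, so they can be tabulated by arm. A reader might infer that the trial cannot address side effects at all. The documents do not support that. They support a narrower statement: no prespecified outcome or comparison, and late, undated recall.

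Three other strong readings also fail.

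- A reader might say that POD#7 lies outside the opioid window. Day 7 opioid use is itself a secondary outcome and is compared in Section 12. The call is late for early events, but it is within the period the trial measures.
- A reader might say that the early contacts record only pain and opioid use. Satisfaction at 24 h, sleep and the walk test on POD#1 are also collected. None of these is a side effect.
- A reader might say that late recall pulls any difference towards zero. That needs recall error to be alike in both arms, and the documents give no information on this.

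It can also be said that Section 13 monitors all adverse events and that the diary might include side effects. Section 13 sets out safety reporting, with no scheduled query and no arm comparison. The diary elements are undefined. Neither supplies a comparative endpoint.

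The objection that 20 per arm is too few stands. Earlier collection dates the events, but it does not make the estimate precise.

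**Conclusion.** The point holds in this limited form. One clause of the hypothesis has no listed outcome and no planned comparison, and its only scheduled data are recalled on day 7, about five days after the 48 h assessment. Early events in the 24 to 48 h window cannot then be told apart from later ones.

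The primary outcome, its test and the purpose in Section 2 are unaffected. A change is worth making because it is cheap and settles a mismatch in the text, but the gain is modest. Even with prompt collection, the difference would be known only to about ±30 percentage points under the assumed rates, and power would be roughly 8% to 16% in the two scenarios worked. The conclusion about outcomes, timing and analysis rests on the text alone. Only the precision figures depend on assumed rates.

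**What to change.** 1. Add a short yes/no checklist of opioid-related side effects (for example nausea or vomiting, itching, sedation) to the existing PACU, 6, 24, 36 and 48 h assessments.
2. In Section 4, list any opioid-related side effect to 48 h as a secondary outcome.
3. In Section 12, state that it will be reported as a difference in proportions with a 95% CI, as descriptive estimation.
4. Keep the POD#7 query for later events and block complications. Early weakness or numbness may be recorded for safety, but should not be attributed to the genicular block: all patients also have a spinal anaesthetic, an IPACK injection and an adductor canal catheter.
5. If no data are to be added, remove the side-effect clause from the hypothesis in Section 3.

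The cost is a few REDCap fields, about a minute per contact, and one line each in Sections 4 and 12. No visits, staff or patients are added. The limitation to state openly is the low precision with 20 per arm.

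### Adverse events are actively sought once, on the POD#7 call; the plan specifies no way to find later harms, to follow a deficit still present that day, or to cover subjects who are not reached

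*Combined protocol and SAP*

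**What the plan says.** Section 10 names the risks of the study injection: "Risks associated with the nerve block include bleeding, infection, and nerve damage". Under Section 4 both arms receive injections at three genicular sites, one with bupivacaine and dexamethasone and the other with saline.

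Section 4 (Postoperative Evaluation) lists six evaluation points: PACU, 6, 24, 36 and 48 hours, and POD 7. Their stated content is pain and opioid use: "Evaluation of both pain intensity (NRS-11 pain scale) and interval opioid consumption will be undertaken at the following time points in a blinded fashion". Adverse events come in separately and once: "Occurrences of adverse events reported by subjects will also be collected during the phone interview on POD#7". The next sentence sets the scope of the interview: "Subjects will be queried as to any block related complications (e.g., prolonged motor blockade or numbness) and opioid-related adverse events". Subjects also keep a diary. Section 4 links it to opioid use and pain after discharge and does not say that it records adverse events.

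Section 13 adds a general duty: "PI will be monitoring all AEs and submitting reports to the IRB per DUHS IRB policy". It also requires prompt reporting of "all unanticipated problems involving risks to subjects or others that occur in the course of a" subject's participation. Section 12 describes the analysis of pain, opioid use, sleep and satisfaction; it does not mention adverse events.

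**The concern.** The stated risks and the collection of safety data do not fit closely. Two of the three risks in Section 10 are not named in the interview. The only scheduled query is also the last scheduled contact, and it depends on the subject being reached and on what the subject chooses to report.

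The clearest case is a subject who is still numb or weak on POD#7, which is the very finding that the interview gives as its example. The event is recorded as present, and nothing in the plan asks what became of it. A slow recovery and a lasting injury then look the same in the data. In a trial whose active solution adds dexamethasone to the local anaesthetic, a reader will want to know whether such a deficit resolved.

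What is at stake is the safety paragraph of the eventual report, not the primary comparison.

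**Working it through.** The point is settled by reading the text. The plan gives no safety figure to reproduce, and none is needed.

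**Step 1. When are adverse events sought?** Of the six evaluation points in Section 4, five (PACU to 48 hours) carry pain and opioid items only. The sixth, POD 7, carries the adverse-event interview. That is one scheduled query, with none after it.

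**Step 2. What does that query cover?** Set Section 10 beside the interview sentence:

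| Risk in Section 10 | Within the open question? | Asked about by name? |
|---|---|---|
| Nerve damage | Yes | In part, through the motor-block and numbness examples |
| Bleeding | Yes | No |
| Infection | Yes | No |

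The middle column is yes throughout because the two examples only illustrate a question about all complications of the block, and because the sentence before it takes in subject-reported adverse events generally.

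**Step 3. Who decides what counts?** The prompt is framed around complications of the block. By POD#7 each subject has had a spinal, a posterior capsule infiltration, an adductor canal catheter, the study injections and a knee replacement (Section 4). A subject with a haematoma or an infected knee may put it down to the operation and not mention it. That is a reasonable inference about how people answer, not something the documents report.

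**Step 4. What happens in the cases that the call does not settle?**

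| Situation | What Section 4 provides | What Section 13 provides |
|---|---|---|
| Deficit present on POD#7 | Recorded that day; no later step stated | PI responsibility; no method or time limit |
| Harm first appearing after POD#7 | No contact scheduled | The same |
| Subject not reached on POD#7 | No second source stated | The same |

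The prompt-reporting clause in Section 13 does not fill these cells. It concerns unanticipated problems during participation, whereas Section 10 already anticipates bleeding, infection and nerve damage, and the last scheduled contact is on POD#7.

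**Step 5. Result.** Events present by POD#7 in a subject who is reached can be captured, with some risk of under-reporting. In the three situations in Step 4 the plan names a responsible person but no source, schedule or end date.

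**The case against.** **The query is open.** A reader might infer that two of the three risks go unprompted. The text does not support that. The interview asks about all block complications and gives two of them as examples, and it also takes general reports of adverse events. This objection stands. What remains is that bleeding and infection are not named and that the subject has to make the attribution.

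**The PI monitors all adverse events.** A reader might also infer that harms after POD#7 are never captured. That goes beyond the text. Section 13 is not tied to POD#7, and it defers to an institutional policy that is not reproduced, so what that policy requires is unknown in either direction. Likewise, the plan does not say that a subject who is numb on POD#7 is not contacted again; it states no rule. The supportable statement is that no means of capture is specified.

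**Safety is not an endpoint, and the trial is too small to establish it.** Largely true. The declared outcomes are opioid use, pain, sleep, satisfaction and walking. Both arms have the same needle placements, and a late infection or persistent numbness would be hard to attribute to them. With zero events the one-sided 95% upper limit is 1 − 0.05^(1/20) = 13.9% for one arm and 1 − 0.05^(1/40) = 7.2% for all 40. These limits depend only on the number of subjects and would be the same with perfect follow-up, so they do not measure this gap. They do show that better collection would give a fuller description of harms, not a safety comparison.

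**A record review assumes that records exist.** The documents do not describe a routine surgical visit or its timing. The review should therefore use whatever record exists at a date that the investigators fix.

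**Conclusion.** The point holds as a limited gap in safety data collection. There is one scheduled adverse-event query, at the last of six evaluation points, with no scheduled contact after it, no step to learn the outcome of a deficit present that day, and no second source for subjects not reached. As a result, a POD#7 deficit cannot be classed as transient or lasting, and harms that appear or persist afterwards have no specified means of capture.

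The documents give no event rate or rate of missed calls, so the number of events that would be lost cannot be estimated, and none is claimed here. The conclusion assumes that the protocol is followed as written and that no follow-up procedure exists elsewhere; the institutional policy cited in Section 13 could supply one. The primary outcome, the sample size and the efficacy analyses are untouched. This is a cheap improvement, not a flaw in the comparison.

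**What to change.** Amend Section 4, for data collection only:

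1. On the POD#7 call, ask by name and without asking for a cause about bleeding or haematoma, infection, new numbness, new weakness, and any unplanned visit or readmission. Keep the open question as well.
2. For any numbness or weakness present on POD#7, record its outcome by repeat telephone contact until it resolves or until a fixed date set by the investigators.
3. At one fixed date set by the investigators, review the existing medical record of all 40 randomised subjects, including those not reached, for bleeding, infection, nerve injury, reoperation and readmission.
4. Have the blinded research team member record these items, and add a line to Section 12 that they will be tabulated by arm, descriptively and without a test.

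The cost is a few REDCap fields, 40 record reviews, repeat calls only to subjects with a deficit on POD#7, and a later study close-out. No new staff, study visit or procedure is needed.

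### The opioid exclusion can admit some preoperative opioid users, and the primary analysis has no planned stratification or adjustment for them: a loss of precision at 20 per arm, not a bias

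*Combined protocol and SAP*

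**What the plan says.** Section 5 (Criteria for exclusion) removes patients with "Chronic opioid consumption (daily morphine equivalent of >30 mg for at least four weeks prior to surgery". This is a single criterion with a dose limit and a duration limit. The next item excludes "History of chronic pain", without a definition. No other criterion concerns recent opioid use.

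Section 4 gives the primary outcome as "Cumulative opioid consumption at 24 hours", with no reference to preoperative intake. On allocation it says "Subjects will be randomized on the morning of surgery" and "40 subjects will be recruited (see #6 Recruitment and Compensation below), 20 in each group"; stratification is not mentioned.

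Section 12 says the primary outcome "will be assessed via two-sided two-sample t-test". It adds "Outcome data distribution will be assessed for normality and log-transformed if necessary". Covariates enter only conditionally: "If differences in key patient factors are identified between groups we will pursue a multivariable linear model". Those factors are not listed, and preoperative opioid use is not mentioned.

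**The concern.** Preoperative opioid intake is a baseline variable measured in the same units as the primary outcome and may well predict it. The exclusion limits that variable only partly. A patient above 30 mg/day for three weeks is not caught by the opioid criterion, and neither is one at 30 mg/day for years.

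Nothing later in the plan reliably takes over. Allocation is not described as stratified, the primary test has no covariate, and adjustment depends on a difference being noticed in factors that are not named in advance.

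Two things are at stake with 20 per arm: a wider outcome distribution, hence less power, and a chance surplus of users in one arm that moves the estimated difference.

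**Working it through.** **Inputs from the documents.** 20 per arm; a 30% difference to be detected (Section 12); two-sided t-test. The control mean, SD, alpha and power are not stated, so the 20 per arm cannot be reproduced.

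**Assumptions.** Alpha 0.05; 80% power; control mean 40 mg; a fraction f of subjects are preoperative users, each taking x mg more in 24 h than they otherwise would. Ranges for f and x are shown below.

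**Step 1: the variability that 20 per arm implies.** By the noncentral t distribution, 20 per arm gives 80% power at a standardised difference of 0.909. The implied coefficient of variation is 0.30 / 0.909 = 0.330 (0.285 if 90% power was intended). On a 40 mg mean the SD is 0.330 × 40 = 13.2 mg and the effect is 0.30 × 40 = 12 mg.

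**Step 2: power with users enrolled.** Take 13.2 mg as the SD within users and within non-users. The overall SD is then √(13.2² + f(1 − f)x²).

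| f | x (mg) | SD (mg) | 12/SD | Power of the planned t-test |
|---|---|---|---|---|
| 0 | – | 13.20 | 0.909 | 80% |
| 5% | 15 | 13.60 | 0.882 | 78% |
| 5% | 30 | 14.73 | 0.815 | 71% |
| 10% | 15 | 13.95 | 0.860 | 76% |
| 10% | 30 | 15.98 | 0.751 | 64% |
| 20% | 15 | 14.50 | 0.828 | 72% |
| 20% | 30 | 17.84 | 0.673 | 55% |

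Example: f = 10%, x = 30 gives √(174.24 + 0.09 × 900) = √255.24 = 15.98. Simulation with exactly 4 users of 40 gave 62% to 64% for this case. With the coefficient of variation held at 0.330, only the ratio of x to the control mean matters: +30 mg on an 80 mg mean gives the same power as +15 mg on 40 mg.

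**Step 3: chance imbalance.** With K users among 40 and simple allocation of 20 per arm, the number in one arm is hypergeometric. The probability that the arms differ by 4 or more users is:

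- K ≤ 3: 0, since it is impossible
- K = 4: 2 × (20 × 19 × 18 × 17) / (40 × 39 × 38 × 37) = 0.106
- K = 8: 0.235
- K = 12: 0.301

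Half of each probability lies in each direction. A difference of 4 users shifts the mean difference by (4/20) × x, which is 3 mg for x = 15 and 6 mg for x = 30. These are a quarter and a half of the assumed 12 mg effect. The 6 mg shift would be all of a 30% effect on a 20 mg mean (6 mg) and a quarter of one on an 80 mg mean (24 mg).

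**Step 4: bias or not.** In a separate simulation with no treatment effect, 5% or 10% of subjects used two or three times as much opioid as the rest. The t-test's type I error was 4.2% to 4.8%. The test stays valid; what is lost is precision.

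**Step 5: what recovers the power.** Simulation with 4 users of 40, x = 30, SD 13.2 mg and effect 12 mg:

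- plan as written: power 62% to 64%
- stratified allocation, still the unadjusted t-test: about 65%, with type I error below 2%
- stratified allocation with the stratum in the model: about 80%

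Stratifying without adjusting recovers little, because the between-stratum variance stays in the t-test's error term.

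**The case against.** The criterion is labelled as chronic consumption and defines it by dose and duration. It does what its label says and removes sustained higher-dose users. A reader might infer that it is an error, or that it fails at its purpose. The documents do not support that, because they nowhere set out to remove every opioid-exposed patient.

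A reader might also infer that the three-week high-dose patient, or the one at 30 mg/day for years, is simply eligible. That goes too far, since the chronic pain exclusion could remove either of them. It is undefined, however. Read narrowly it leaves the gap open; read broadly it could exclude much of an elective knee replacement population.

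Section 12 does provide for a multivariable model if groups differ, and for a log transformation. The conditional model could address a noticed imbalance, but it does not name preoperative opioid use or say what counts as a difference. It is also not aimed at the variance users add when the arms are balanced. A log transformation may reduce skew but does not remove imbalance.

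The calculations cover preoperative users of any kind, not only those admitted by the joint threshold, whose number is unknown. The institutional experience behind the sample size may already include such patients; part or all of the power loss would then be built in, and adjustment would be a gain in power. It is also tempting to say that a user's usual daily dose counts in full as postoperative consumption. Section 4 describes as-needed fentanyl and oxycodone and does not say whether home opioids are continued or counted, so x is an assumption. All these limits stand. They reduce the certainty about size, not the case for a cheap safeguard.

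**Conclusion.** The point holds as a matter of precision and chance imbalance. Some preoperative opioid users can be enrolled, and neither the allocation nor the primary test is planned to account for them. A reader might infer a biased comparison; randomisation rules out systematic bias, and the simulated type I error agrees.

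Under the stated assumptions the cost runs from negligible (80% to 78% power with 5% of subjects at +15 mg) to substantial (55% with 20% at +30 mg). The documents give no user prevalence, excess intake, control mean or SD, so the range cannot be narrowed, and Section 12 shows no margin to absorb a loss. This is an inexpensive improvement to the design and primary analysis. It is not a contradiction in the protocol and not a reason to change who is eligible.

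**What to change.** 1. Record preoperative opioid dose and duration at screening. Applying the existing criterion already requires asking.
2. Stratify randomisation by any opioid use in the four weeks before surgery (yes/no).
3. Make the primary analysis a linear model of 24 h consumption, on the log scale if needed, with treatment and that stratum as terms. Prespecify it in place of the unadjusted t-test, not conditional on an observed imbalance. If no users enrol, the model reduces to the t-test.
4. Have the investigators confirm that the dose and duration limits are meant jointly, define the chronic pain exclusion, and reconcile the two. No new threshold is proposed.

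Cost: protocol wording, one screening item, a two-stratum list and one degree of freedom; no extra visits and no loss of eligible patients. Item 2 should not be adopted without item 3: stratifying and then ignoring the stratum makes the t-test conservative and recovers little power.
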